7.1.1.8.3 Dispense Glucose Meter and SMBG Instructions

The activities in this section will occur at **Visit 2/Week -2** for subjects who are not undergoing washout. They will occur at **Visit 1A/Washout** for subjects who are undergoing washout.

Glucose meters and Fingerstick Glucose Logs will be supplied to all subjects in order to perform SMBG. Subjects will be instructed on the procedure to perform fingerstick glucose measurements. Subjects will monitor their fingerstick glucose concentrations with a frequency determined appropriate by the investigator (based upon his/her assessment of the subject's risk of increasing glucose concentrations) with a minimum of two fasting determinations per week.

From the time the glucose meters are supplied, through Visit 3/randomization, subjects should be counseled to contact the trial site if fasting fingerstick glucose levels are above 260 mg/dL (14.4 mmol/L) \geq 2 times per week. Subjects will also be instructed to contact the site if their fingerstick glucose values are \leq 70 mg/dL (\leq 3.9 mmol/L).

Furthermore, in order to assess the need for discontinuation from investigational product, subjects should be instructed to contact the site for fasting fingerstick glucose values that are >270 mg/dL (15.0 mmol/L) after Visit 3/Randomization (Day 1) through Visit 8/Week 6, or >240 mg/dL (13.3 mmol/L) after Visit 8/Week 6 through Visit 10/Week 12.

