5.2.3 Trial Blinding/Masking

A double-blind/masking technique will be used. MK-8521 and placebo will be packaged identically so that blind/masking is maintained. The subject, the investigator and Sponsor personnel or delegate(s) who are involved in the treatment or clinical evaluation of the subjects are unaware of the group assignments.

The liraglutide treatment arm will be open-label therefore, the Sponsor, investigator and subject will know the treatment administered.

See Section 7.1.4.2, Blinding/Unblinding, for a description of the method of unblinding a subject during the trial, should such action be warranted.

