7.1.1.8.2 Dispense Hypoglycemia Assessment Log and Instruct on Hypoglycemia Symptoms and Management

The activities in this section will occur at Visit 2/Week -2 for subjects who are not undergoing washout. They will occur at Visit 1A/Washout for subjects who are undergoing washout.

The site will review the symptoms and management of hypoglycemia with the subject. The site will counsel the subject to immediately perform a fingerstick glucose measurement if any symptoms occur that may be related to hypoglycemia (e.g., weakness, dizziness, shakiness, increased sweating, palpitations, or confusion), but also to avoid delay in treating these symptoms.

The subject will be instructed to complete the Hypoglycemia Assessment Log (HAL) for any symptomatic episodes he or she believes may represent hypoglycemia. If a fingerstick glucose has been obtained before or shortly (i.e., within a few minutes) after treating, the value should be recorded in the log. In addition, subjects will be instructed to record in the log any fingerstick glucose values ≤ 70 mg/dL (3.9 mmol/L) regardless of the presence of symptoms.

Subjects should be instructed to contact the investigational site to report:

- Any episode of hypoglycemia for which assistance was required (i.e., severe hypoglycemia).
- Any episode of fingerstick glucose ≤70 mg/dL (3.9 mmol/L) with or without symptoms.

Note: As indicated, subjects will record symptoms and/or fingerstick glucose measurements that they believe are related to hypoglycemia on the HAL. Each episode should be evaluated by the investigator. For episodes determined to be hypoglycemia (symptomatic or asymptomatic), and for all glucose values ≤70 mg/dL (3.9 mmol/L) regardless of whether they are considered an adverse event, the Hypoglycemia Assessment (HA) eCRF must also be completed. Each event of symptomatic hypoglycemia must be reported as an adverse event on the adverse eCRF. Each episode

of asymptomatic hypoglycemia considered by the investigator to be an adverse event should also be reported on the adverse event eCRF (see Section 7.1.2.10.2.1 for guidance on reporting).

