7.1.2.10.2 Hypoglycemia

Based on review of the subject-completed HAL at each clinic visit to the site, the investigator must assess the glucose values as well as any symptoms of hypoglycemia reported by the subject.

7.1.2.10.2.1 Reporting Events of Hypoglycemia

All episodes considered as likely to represent symptomatic hypoglycemia by the investigator should be captured as an adverse even of "symptomatic hypoglycemia." This diagnosis may be supported by, *but does not require*, confirmatory blood glucose results (such as those

70

Protocol/Amendment No.: 004-02

Product: MK-8521

measured using a fingerstick or from a clinical laboratory sample). Further, at the discretion of the investigator, an asymptomatic blood glucose value ≤70 mg/dL (3.9 mmol/L) may be reported as an adverse event of "asymptomatic hypoglycemia." General guidance regarding the determination as to whether an event is considered to be an adverse event should be followed (see Section 7.2).

Regardless of whether an episode is considered an adverse event, the HA eCRF *must* be completed for the following:

- all episodes determined by the investigator to be hypoglycemia (symptomatic or asymptomatic).
- all glucose values \leq 70 mg/dL (3.9 mmol/L).

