7.1.5.4.3 Run-in (Visit 2/Week-2)

Subjects' prior/concomitant medications and adverse events will be reviewed. Vital signs, body weight, and height will be measured and laboratory samples will be obtained.

Note: If Visit 2/Week -2 occurs ≤2 weeks after Visit 1/Screening, it is not necessary to repeat A1C, hematology and chemistry panel tests at Visit 2/Week -2. The Visit 1 results from these assessments may be used to satisfy entry criteria (see Section 6, Trial Flow Chart).

A full physical exam, locally read 12-lead ECG and postural blood pressure and pulse will be performed.

All non-washout subjects (these subjects will not have a Visit 1A) will (1) have diet/exercise counseling, (2) receive glucose meters and training in performing SMBG, and (3) receive instruction on hypoglycemia symptoms, hypoglycemia management, and completion of the HAL.

All non-washout subjects will be instructed to monitor their fingerstick glucose concentrations with a frequency determined appropriate by the investigator (based upon his/her assessment of the subject's glycemic control) with a minimum of two fasting determinations per week.

Subjects undergoing AHA washout (who previously received dietary counseling/glucose meters/SMBG training/HAL training at Visit 1A) will have SMBG measurements, and HAL reviewed at Visit 2/Week -2. Appropriate die/exercise counseling will also be performed.

See sections 5.7.1 and 7.1.1.8.2 and 7.1.1.8.3 for additional information regarding dietary/and exercise counseling, HAL training and SMBG training, respectively.

Subjects who meet all enrollment criteria applicable through Visit 2/Week-2 (as detailed in Section 5.1) will enter the 2-week, single-blind, placebo run-in period. The placebo run-in may be initiated at Visit 2/Week -2 while laboratory data, including A1C, are pending, but randomization may not occur until all eligibility criteria are confirmed.

The first doses of single-blind placebo must be taken as witnessed doses in the clinic visit after completion of all **Visit 2/Week -2** procedures and fasting blood samples. Subjects will then be dispensed single-blind investigational product (MK-8521 180 µg and MK-8521 300 µg matching placebos) and instructed to take one injection (0.1 mL) per day from each vial at approximately the same time of day in the morning for two weeks prior to randomization. Subjects should be reminded to withhold single-blind investigational product on the day of **Visit 3/ Day 1**.

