Tier 2 ¹	Change from baseline in HR		X	X
	HR >100 bpm or HR increase >30 bpm		X	X
	AE summary measures		X	X
	Specific AEs ² , SOCs, specific confirmed CV SAEs, and PDLCs		X	X
Tier 3	All endpoints listed under Tier 2 (above) that have incidence <4 subjects in all treatment groups			X
	Additional hypoglycemia adverse event endpoints			X
	Change from baseline results (laboratory measurements, ECG, and vital signs)			X

¹ Non-continuous endpoints listed here will qualify for Tier 2 only if the incidence is ≥4 subjects in at least one of the treatment groups.

Analysis of Hypoglycemia

The Tier 1 analysis for hypoglycemia will include the numbers and percentages of subjects experiencing one or more adverse events of symptomatic hypoglycemia, regardless of glucose value.

The Tier 2 analysis for hypoglycemia will include the numbers and percentages of subjects experiencing one or more of each the following:

- Adverse events of hypoglycemia (symptomatic or asymptomatic), regardless of biochemical documentation.
- Adverse events of documented hypoglycemia, defined as adverse events of symptomatic hypoglycemia with a concurrent glucose measurement of <70 mg/dL (<3.9 mmol/L)

² Among those endpoints not pre-specified as Tier 1 endpoints.

AE=Adverse Event; CI=Confidence Interval; ECG=Electrocardiogram; PDLC=Pre-Defined Limit of Change;

SAE=Serious adverse event; SOC=System Organ Class; X = results will be provided.

Product: MK-8521

Protocol/Amendment No.: 004-02

 Adverse events of severe hypoglycemia, defined as adverse events of symptomatic hypoglycemia that required assistance, either medical or non-medical, regardless of whether such assistance was obtained, and regardless of biochemical documentation. These events will be further sub-classified as:

- Those that required medical assistance. Adverse events of symptomatic hypoglycemia that included a markedly depressed level of consciousness, loss of consciousness, or seizure will be classified as having required medical assistance, whether or not medical assistance was obtained
- Those that did not require medical assistance (i.e., those episodes that required non-medical assistance to treat).

The Tier 3 summary of hypoglycemia will include the following, based on episodes classified by the investigator as adverse events:

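### One Tier 2 hypoglycemia item counts asymptomatic lows only if the investigator calls them adverse events, and that investigator knows who is on liraglutide

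*Combined protocol and SAP*

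**What the plan says.** **Testing.** Section 7.1.1.8.3 has subjects monitor fingerstick glucose "with a frequency determined appropriate by the investigator (based upon his/her assessment of the" individual. The criterion named is that person's "risk of increasing glucose concentrations) with a minimum of two fasting determinations per week". The run-in instructions in Section 7.1.5.4.3 keep the same floor but name a different basis: the investigator's "assessment of the subject's glycemic control) with a minimum of two fasting determinations per week". Both instructions are given before randomization. Nothing fixes the frequency afterwards or varies it by arm. Separately, Section 7.1.1.8.2 applies to everyone: "The site will counsel the subject to immediately perform a fingerstick glucose measurement if any symptoms occur".

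**Classification.** Section 7.1.1.8.2 states: "Each event of symptomatic hypoglycemia must be reported as an adverse event on the adverse eCRF". For asymptomatic values, Section 7.1.2.10.2.1 says that "at the discretion of the investigator, an asymptomatic blood glucose value ≤70 mg/dL (3.9 mmol/L) may be reported as an adverse event". The Hypoglycemia Assessment (HA) eCRF is mandatory for every value of 70 mg/dL or below, adverse event or not.

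**Blinding.** Section 5.2.3: "The liraglutide treatment arm will be open-label therefore, the Sponsor, investigator and subject will know the treatment administered". MK-8521 and placebo are double-blind.

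**Analysis.** Section 8.2.5.2 lists three Tier 2 hypoglycemia items. The first is "Adverse events of hypoglycemia (symptomatic or asymptomatic), regardless of biochemical documentation". The other two, documented and severe hypoglycemia, are restricted to symptomatic adverse events, as is the Tier 1 item. Tier 2 items get 95% CIs for each MK-8521 dose versus placebo and versus liraglutide, provided at least 4 subjects in some group have the event. HA eCRF episodes not called adverse events get a summary. Fuller Tier 3 tables are optional, and depend on there being many such subjects, a condition left undefined.

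**The concern.** An asymptomatic low value passes two steps before it counts in the first Tier 2 item: someone has to test, and the investigator has to call the result an adverse event.

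The second step is discretionary. In the liraglutide arm it is taken by someone who knows the treatment; in the MK-8521 arms it is not. A difference between MK-8521 and liraglutide on this item could therefore reflect how episodes were labelled rather than how often they happened. The direction cannot be predicted from the documents.

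The first step matters for the placebo comparison as well. A testing frequency keyed to rising glucose could send extra tests to subjects with poorer control, plausibly more often on placebo. If so, lows on MK-8521 would be found less completely, which would tend to hide an excess.

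At stake is the reading of one supportive safety item. No hypothesis test depends on it.

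**Working it through.** **1. The plan's own figure.** Section 8.2.5.2 says that with equal arms and fewer than 4 events in each, the 95% CI for the difference always includes zero. Taking the extreme split at 40 per arm (Section 8.2.7) with the Miettinen-Nurminen interval:
- 3 versus 0 of 40: -1.7 to 20.0 points, includes zero
- 4 versus 0 of 40: 0.7 to 23.2 points, excludes zero

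The threshold reproduces. A shift of one or two subjects can decide whether the item gets a CI at all.

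**2. Which endpoints are exposed.**

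| Endpoint | Symptoms required | Adverse-event status |
|---|---|---|
| Tier 1 symptomatic hypoglycemia | yes | mandatory |
| Tier 2 any hypoglycemia | no | discretionary for the asymptomatic part |
| Tier 2 documented | yes | mandatory |
| Tier 2 severe | yes | mandatory |

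Only the asymptomatic part of the second row depends on both routine testing and discretion. Judging whether an episode is symptomatic hypoglycemia still rests with the investigator in every row.

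**3. Classification, illustrated.** Assumption: 10% of each arm (4 of 40) has a detected asymptomatic low. The documents give no rate. With a share c called adverse events, the expected incidence is 10% × c, and the chance of reaching 4 of 40 is a binomial tail:
- c = 25%: 2.5%, chance 0.02
- c = 50%: 5%, chance 0.14
- c = 100%: 10%, chance 0.58

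If c is 50% in one arm and 100% in the other, the apparent difference is 10 - 5 = 5 points; at 25% versus 100% it is 10 - 2.5 = 7.5 points. The true difference in both cases is zero.

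**4. Detection, illustrated.** Assumption: each fasting reading has the same chance q of being 70 mg/dL or below, in every subject and arm. With k readings a week over 12 weeks, the share with at least one detected low is 1 - (1 - q)^(12k):

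| q | k = 2 (floor) | k = 3 | k = 7 |
|---|---|---|---|
| 0.001 | 2.4% | 3.5% | 8.1% |
| 0.002 | 4.7% | 7.0% | 15.5% |
| 0.005 | 11.3% | 16.5% | 34.4% |
| 0.01 | 21.4% | 30.4% | 57.0% |

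Only the column for k = 2 is anchored in the protocol. The table shows that the item is sensitive to testing frequency. It does not show that frequency would differ by arm.

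**5. Sensitivity of laboratory FPG.** Section 6.0 schedules post-randomization FPG at Weeks 1, 2, 3, 4, 6, 9 and 12 in every arm, about 7 of 84 days. One randomly placed low day is caught with probability 7/84 = 8%, and at least one of two with 1 - (77/84)^2 = 16%. At the self-testing floor the figures are 2/7 = 29% and 1 - (5/7)^2 = 49%. FPG has the same schedule in all arms but is less sensitive.

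**The case against.** **Unequal testing is not prescribed.** The floor, the symptom rule and the logging rule are identical in all arms, and the frequency is first set before randomization. This stands: the plan permits unequal testing but does not call for it.

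**The mechanism partly cancels itself.** Subjects tested more because their glucose is rising are the least likely to have low values, while a well-controlled placebo subject probably tests at the floor too. This also stands. A reader might infer that about half of the subjects with two low days are missed on MK-8521 and none on placebo (49% versus 100% detection). That contrast needs daily testing in one arm and floor testing in the other, and no section supports daily testing.

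**Little may reach the analysis.** Section 4.1.2.2 describes hypoglycemia risk as low. Sulfonylureas are washed out, a fasting fingerstick below 130 mg/dL at Visit 3 is exclusionary, and Section 8.2.5.2 treats Tier 2 intervals as flags rather than formal tests. All true, and it keeps the point small.

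**The plan already has a backstop.** The HA eCRF is mandatory and the summary of non-adverse-event episodes is unconditional, so unequal labelling could be seen. It would be seen without any between-arm interval, however, and the fuller tables remain optional. Section 4.2.3.1 concedes that knowing the treatment may confound liraglutide comparisons, but says so about efficacy and offers nothing for this item.

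**Conclusion.** The point holds in a narrow form. The asymptomatic part of one Tier 2 item is open to differential classification in the MK-8521 versus liraglutide comparison. Versus placebo, classification is blinded, and what remains is a possible difference in detection through the self-testing rule. The documents allow neither effect to be quantified. The 5 to 7.5 points in the classification illustration rest wholly on the assumed 10% rate and assumed labelling shares.

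Three stronger readings are tempting and are not supported. Tier 2 hypoglycemia as a whole is not compromised, because the documented and severe items, like Tier 1, require symptoms, which prompt testing and mandatory reporting. Knowledge of treatment does not bias the placebo comparison. And nothing shows that low glucose will in fact be sought or counted unequally; the plan leaves that possible. This is an inexpensive improvement, not a threat to the trial's conclusions.

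**What to change.** In Section 8.2.5.2, before unblinding:

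1. Keep the existing adverse-event item. Add a Tier 2 item, under the same 4-subject threshold, for subjects with any post-randomization HA eCRF episode that is symptomatic or has a glucose of 70 mg/dL or below, regardless of adverse-event status. Make it unconditional, in place of the optional tables.
2. Add the proportion of subjects with any scheduled post-randomization central-laboratory FPG of 70 mg/dL or below (Weeks 1, 2, 3, 4, 6, 9, 12), and state its low sensitivity.
3. Reconcile three wordings: the two bases for self-testing frequency (Section 7.1.1.8.3 versus Sections 7.1.5.4.2 and 7.1.5.4.3); the documented-hypoglycemia cut-off, strictly below 70 mg/dL in Section 8.2.5.2 but 70 or below elsewhere; and Table 13, which puts additional hypoglycemia endpoints in Tier 3 while the text lists three in Tier 2.

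The cost is SAP wording and two more table rows; the data are already collected in every arm. More episodes, mostly minor, will be counted. The HA eCRF item removes discretion over labelling low values but does not correct for unequal self-testing. The FPG item has equal ascertainment by schedule, but only on visit days.

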7.1.1.8.4 Witnessed Dosing

Administration of investigational product (blinded or open-label) will be witnessed by the investigator and/or trial staff at all clinic visits (when investigational product administration is continuing) after completion of all trial procedures including the collection of all fasting blood samples.

7.1.1.8.5 Dispense Single-Blind Placebo Run-in Investigational Product

Subjects will be dispensed single-blind investigational product (MK-8521 300 µg and MK-8521 180 µg matching placebos) at **Visit 2/Week -2** and instructed to take one injection (0.1 mL) per day from each vial at approximately the same time of day in the morning. The last dose of placebo run-in should be taken on the day prior to **Visit 3/Day 1**.

Refer to Section 5.2.2 for further details.

7.1.1.8.6 Dispense Double-Blind/Open-Label Investigational Product

Subjects will be dispensed double-blind investigational product at all treatment visits from **Visit 3/Day 1** through **Visit 9/Week 9**. Open-label liraglutide can be dispensed such that the subject will not run out prior to the next trial visit. Suggested liraglutide dispensing guidance can be found in Table 8.

Protocol/Amendment No.: 004-02

Table 8 Suggested Liraglutide Dispensing Guidance

Visit #/Week # (window)	# of Liraglutide Pens Dispensed								
Visit 3/Day 1 (14 days)	1 ^a								
Visit 5/Week 2 (7 days)	1								
Visit 6/Week 3 (7 days)	1								
Visit 7/Week 4 (14 days)	2								
Visit 8/Week 6 (21 days)	3								
Visit 9/Week 9 (21 days) 3									
One 18-mg pen is sufficient (0.6 mg x 6 days + 1.2 mg x 7 days = 12 mg used) to									

one 18-mg pen is sufficient (0.6 mg x 6 days + 1.2 mg x / days = 12 mg used) to cover the liraglutide titration period (Visit 3 to Visit 5).

Subjects randomized to MK-8521 (either dose) or placebo should be instructed to take one injection subcutaneously per day **from each vial** in the morning at approximately the same time each day.

Subjects randomized to liraglutide should be instructed to take one injection subcutaneously per day in the morning at approximately the same time each day.

Refer to Section 5.2.2 for further details.

7.1.1.8.7 Medication Compliance Monitoring

Subjects will be directed to bring all vials/pens (used and unused) to each visit. The investigator must maintain a complete and current accountability record for the investigational product.

Compliance with the placebo run-in medication should be monitored by study personnel at the site at the end of the placebo run-in at Visit 3/Day 1. Compliance should be assessed by all of the following:

- 1. subject report
- 2. used vial count
- 3. estimation of used vial volume (when compared to an unused vial).

Subjects who miss more than one daily dose (i.e., 2 injections on the same day or 2 single injections on separate days) of the placebo run-in medication are ineligible for randomization.

During the remainder of the trial, compliance with blinded investigational product will be assessed using the same approach noted above: (1) subject report, (2) used vial count and (3) estimation of vial volume as compared to an unopened vial.

For subjects randomized to open-label liraglutide, compliance will be assessed based on (1) subject report and (2) visual inspection of used pen(s).

Protocol/Amendment No.: 004-02

Every effort will be made to maintain compliance at 100%:

• The investigator or designee will counsel subjects who report taking <100% of the prescribed investigational product following randomization.

- The investigator or designee will determine factors that resulted in <100% compliance with the investigational product and will take steps to improve compliance.
- Subjects will be counseled on the importance of taking their medication as prescribed.
- Subject counseling will be documented in source documents.

7.1.2 Clinical Procedures/Assessments

7.1.2.1 Vital Signs (Sitting Blood Pressure and Heart Rate)

Vital sign measurements include a triplicate measurement of sitting blood pressure and heart rate. Blood pressure and heart rate will be measured using an automated, oscillometric blood pressure measuring device at all visits as noted in the Trial Flow Chart - Section 6.0. Site personnel should use the same blood pressure measuring device throughout the study for each subject.

The following method should be used to record sitting blood pressure and heart rate for subjects in triplicate:

- Subjects will refrain from ingesting caffeine for at least 10 hours preceding the measurements.
- Subjects should be seated in a chair with their back supported, feet flat on the floor and arm bared (free of restrictions such as rolled up sleeves) and supported at heart level
- The appropriate cuff size must be used to ensure accurate measurement. Each subject's cuff size should be noted in his/her source file to assure the same cuff size is used throughout the trial.
- Measurements should be taken on the same arm at each visit (preferably the non-dominant arm).
- Measurements should begin after at least 5 minutes of rest.
- The three measurements of both the blood pressure and heart rate must be taken approximately 2 minutes apart.
 - Note: Measurements will be collected until the 3 consecutive systolic BP readings do not differ by more than 5 mm Hg of each other and the 3 consecutive diastolic BP readings do not differ by more than 5 mm Hg of each other with the last triplicate set recorded in the eCRFs.
 - The mean (average) of the last triplicate set of BP readings (at Visit 1 and if necessary, at Visit 3) will be used to determine eligibility.

Protocol/Amendment No.: 004-02

 Assessment of heart rate can be manual (rather than using an automated device); however, when done manually, heart rate must be measured in the brachial/radial artery for at least 30 seconds.

- Note: Measurements will be collected until the 3 consecutive heart rate readings do not differ by more than 5 bpm of each other with the last triplicate set recorded in the eCRFs.
- The mean (average) of the last triplicate set of heart rate readings will be used to determine eligibility (Visit 1, Visit 2, and Visit 3), baseline HR (Visit 3), and discontinuation criteria (all post-randomization visits).

Other procedures should not be performed during the time of the blood pressure and heart rate measurements.

